### 9.5.2 Unexpected Events

Unexpected events are those considered unexpected when it varies in nature, intensity or frequency from the information provided in the current adverse event list, the IB, the package insert or when it is not included in the ICF as a potential risk.

## 9.6 ASSESSMENT OF RELATIONSHIP TO STUDY DRUG (CAUSALITY)

Investigators are required to assess the causal relationship (i.e., whether there is reasonable possibility that the study drug caused the event) using the following definitions:

- **Unrelated:** Another cause of the AE is more plausible; a temporal sequence cannot be established with the onset of the AE and administration of the investigational product; or, a causal relationship is considered biologically implausible.
- **Possibly Related:** There is clinically plausible time sequence between onset of the AE and administration of the investigational product, but the AE could also be attributed to concurrent or underlying disease, or the use of other drugs or procedures. Possibly related should be used when the investigational product is one of several biologically plausible AE causes.
- **Definitely Related:** The AE is clearly related to use of the investigational product.

## 9.7 SEVERITY OF ADVERSE EVENTS (GRADING)

AEs will be categorized and graded by the Investigator through use of the CTCAE v 4.0 five-point scale, Grades 1 to 5 with unique clinical descriptions of severity for each referenced AE.

Should a subject experience any AE not listed in the CTCAE v4.0, the following grading system should be used to assess severity:

Table 2. Adverse Event Grading Criteria		
CTCAE Grade	Equivalent To	Definition
Grade 1	Mild AE	Experiences which are usually transient, requiring no special treatment, and no disruption of normal daily activity
Grade 2	Moderate AE	Experiences which introduce some level of inconvenience or concern to the subject, and which may interfere with daily activities, but are usually ameliorated by simple therapeutic maneuvers
Grade 3	Severe AE	Experiences which are unacceptable or intolerable, significantly interrupt the subject's usually daily activity, and require systemic drug therapy or other treatment
Grade 4	Life threatening / disabling AE	Experience which causes the subject to be in imminent danger of death
Grade 5	Death related to AE	Experiences resulting in subject death

## 9.8 DEFINITION OF SERIOUS ADVERSE EVENTS

An SAE is an untoward medical occurrence that at any dose:

- Results in death (the AE actually causes or leads to death)
- Is life-threatening (“life-threatening” is defined as an AE in which the subject was at risk of death at the time of the event. It does not refer to an event which hypothetically might have caused death if it were more severe. If either the Investigator or the Sponsor believes that an AE meets the definition of life-threatening, it will be considered life-threatening).
- Requires in-patient hospitalization or prolongation of existing hospitalization
- Results in persistent or significant disability/incapacity (the AE results in substantial disruption of the subject's ability to conduct normal life functions)
- Results in a congenital anomaly/birth defect
- Is medically significant

Medical and scientific judgment should be exercised in deciding whether other situations, such as important medical events that may not be immediately life-threatening or result in death or hospitalization but may jeopardize the subject or may require intervention to prevent one of the other outcomes listed in the definition above, should also be considered serious. If either the Sponsor or the Investigator believes that the event is serious, the event will be considered serious.

## 9.9 EVENTS OF SPECIAL INTEREST

### 9.9.1 Appearance of Satellite Lesions

If a patient appears with a lesion that is not at the original injection site, the incident will be reported to the Sponsor-Investigator within 24 hours of occurrence using the SAE CRF in REDCap. The subject will be instructed to return to the clinic and the appropriate safety protocol will be followed. The lesion will be swabbed per instructions from BNI and sent to the designated lab for testing. If the lesion comes back positive, it will be reported to the FDA and NIH as outlined in section 9.10.

### 9.9.2 Pregnancy of a Female Partner

For the purposes of this study, pregnancy of a female partner will be captured using a modified SAE report form, however; the event is not considered an SAE but will be reported to the appropriate regulatory authorities in the annual safety update. Partner pregnancies will be followed through the term of the pregnancy or pregnancy termination and the birth of the child after the female partner has signed the Pregnant Partner Informed Consent Form. Subjects and their partners will be counseled as to any possible known risks to either the partner or the child.

### 9.9.3 Accidental Transmission of Vaccinia Virus

Accidental transmission of vaccinia virus to a clinic staff member or a member of the subject's family or personal contacts must be reported to the Investigator as soon as possible, but no later than 24 hours after he/she becomes aware. The Investigator must contact the BNI study Medical Monitor if there are specific questions in regard to the potential vaccinia reaction. A swab of the suspected lesion may be obtained from the study subject for confirmatory testing prior to administration of VIG. The Investigator should refer to the Management Plan for Potential Serious Vaccinia Reaction for recognition, diagnosis and treatment of a rare potential serious vaccinia reaction. This plan also describes when VIG is indicated for use and administration procedures. For further information or for a supply of VIG in the United States, contact the CDC at [contact]. If VIG treatment is warranted, the person receiving VIG must sign the Consent Form to Administer Vaccinia Immune Globulin (VIG) **PRIOR** to administration of VIG.

## 9.10 EXPEDITED REPORTING REQUIREMENTS FOR SERIOUS ADVERSE EVENTS AND EVENTS OF SPECIAL INTEREST

All events described in section 9.8 and 9.9 must be submitted to the SIS Unit within 24 hours of the investigator learning of the event following the SOPs outlined in the CTO 102377 Operations Manual.

The SIS Unit will be responsible for processing these events for reporting to the applicable regulatory and oversight authorities including the IRB, DSMC and FDA.

All SAEs and events of special interest must be reported to Bavarian Nordic, Inc. within 24 hours by fax or email to:

Bavarian Nordic, Inc.  
Attn: Drug Safety and Pharmacovigilance Designee  
[contact]

Email: [[contact]](mailto:[contact])

Any suspected, unexpected SAE, skin lesion positive for vaccinia, pregnancy of a female partner, or accidental transmission of vaccinia virus must be reported to the FDA as soon as possible and no later than 7 days (for a death or life-threatening event) or 15 days (for all other SAEs) after the investigator's or institution's initial receipt of the information.

## **10 STATISTICAL CONSIDERATIONS**

We will compare RFS at two years for the patients treated with PROSTVAC to that of untreated historical controls. A secondary efficacy objective will be a comparison of the observed RFSs for the treated subjects with the calculated RFSs for the same subjects as if they had not received adjuvant therapy .

### **10.1 STATISTICAL CONSIDERATIONS FOR THE PRIMARY OBJECTIVE**

**Endpoint:** The primary endpoint will be a binary indicator of relapse status at the 2 year follow-up visit after prostatectomy. Due to interval-censoring, using a time-to-event RFS outcome may lead us to anti-conservative estimates due to some patients having follow-up weeks to months after the 2 year anniversary of their surgery and recurrences defined at those later timepoints would not be captured in an estimate of 2 year RFS based on a Kaplan-Meier approach. A time-to-event analysis of RFS will also be performed, but not for making inferences for the primary objective. Patients who do not have data available for a two-year follow-up will be censored at the last visit at which they were known to be recurrence-free. Patients who drop out will be replaced for up to 4 patients. However, those who choose to discontinue treatment prior to a recurrence (or other event defined in [Section 4.6](#)) but wish to remain in the study, will be followed through 24 months to evaluate their disease status based on the intent-to-treat principle. These subjects will not be replaced.

**Analysis Plan:** The primary endpoint will be a binary indicator of relapse status at the 2 year follow-up visit after prostatectomy. Two-year RFS will be estimated as a proportion with an exact 95% confidence interval. RFS will also be treated as a time-to-event variable and Kaplan-Meier curves will be created and median and two year RFS will be reported with 95% confidence intervals.

**Sample Size Justification:** To estimate the likelihood of RFS at 2 years for subjects at high risk of relapse, we extracted data from two sources. The first source is a database of high risk subjects that we have previously used in published research (122). The database contains clinical synopses of 243 subjects treated with radical prostatectomy (retropubic, laparoscopic, and perineal) for high-risk prostate cancer. These subjects were treated by multiple surgeons at several academic medical centers. None received any adjuvant therapy. High-risk features included one or more of the following criteria: pre-operative PSA  $\geq$  10 ng/mL; Gleason score 8-10; positive surgical margins, seminal vesicles, extraprostatic extension, or lymph nodes; persistently detectable PSA  $>45$  days after surgery. Relapse-free survival was defined as the interval (days) from prostatectomy to the first of the following: a) PSA of  $\geq$  0.2 ng/mL (confirmed)

>30 days later, b) appearance of lesions consistent with metastases on imaging studies, or c) institution of new prostate cancer therapy. The observed 1yr probability of RFS was 0.751 and the 2yr probability of RFS was 0.645.

An additional source of data for RFS was the ECOG E3886 study (13), in which subjects with node-positive prostate cancer after radical prostatectomy (n = 98) were randomized to immediate ADT, or ADT at the time of clinical relapse. This analysis was performed by [name] (ECOG statistical office) at our request, in 2010. Relapse was defined as the first of the following: a) the appearance of local or distant metastases identified by imaging or physical examination, b) the first increase in PSA  $> 0.1$  ng/mL following a post-prostatectomy PSA nadir of  $< 0.1$  ng/mL or c) death from any cause. The RFS probability curve is shown in Appendix B. The observed 1yr probability of RFS was 0.73 and the 2yr probability of RFS was 0.56.

While the two groups differ somewhat in the disease status of the subjects, as well as frequency and manner of follow up, the probabilities of RFS agree quite closely. For the purposes of our power analysis and sample size, we will assume that the true probability of RFS at 2 years, for patients similar to our proposed study population, is 0.60.

We define an “interesting” reduction in the risk of relapse to be 30% (i.e., increase in the probability of RFS from 0.6 to 0.78). Assuming a one-sided alpha = 0.1, with 30 evaluable patients, we have 80% power to detect this difference based on an exact binomial test. Thus if among 30 evaluable subjects, at least 24 are recurrence free at 24 months, we will reject the null hypothesis (2 year RFS=0.60) and conclude that the PROSTVAC intervention improves RFS relative to the current standard of care in this patient population (one-sided p-value  $\leq 0.025$ ). Anticipating a final sample size of 30 patients with 10% drop out rate, we plan to enroll 33 patients for this study.

**Interim Analysis:** An interim analysis for futility will be performed through Simon’s minimax two-stage design (Simon, 1989) when a total number of 19 patients are evaluable. The design is described as follows:

**Stopping criteria:** Stop the study if there are 11 or fewer recurrence free among the first 19 evaluable patients. Otherwise, additional patients will be accrued resulting in a total evaluable sample size of 30.

**Decision rule at N=30 evaluable patients:** Reject the null hypothesis if there are 22 or more recurrence free among the 30 evaluable patients. We claim that the PROSTVAC intervention improves RFS relative to the current standard of care in this patient population. This design controls the type I error rate at 0.1 and yields the power of 0.8.

**Safety Monitoring:** Continuous safety monitoring will be performed with early stopping rules in the case of unacceptable risk to the subjects, defined as evidence in favor of a risk of a grade 3 or greater toxicity deemed to be possibly related to treated of 25% vs. an acceptable rate of 10%. Stopping criteria are shown in the table below. The stopping rules are based on a likelihood ratio. Specifically, the likelihood ratio is calculated based on a hypothesized 10% event rate (safe) vs, a 25% event rate (unsafe) and likelihood ratios in excess of 8 (in favor of an event rate of 25%)

are considered sufficient evidence to stop the trial. For example, 7 events in 33 patients yields an event rate of 0.21, which has a likelihood ratio of 9.21 favoring a rate of 25% vs. 10%.

Stop if:	Likelihood Ratio	Observed Event Rate
3 events in $\leq 6$ patients	$\geq 9.04$	$\geq 0.50$
4 events in $\leq 12$ patients	$\geq 9.08$	$\geq 0.33$
5 events in $\leq 18$ patients	$\geq 9.13$	$\geq 0.28$
6 events in $\leq 24$ patients	$\geq 9.17$	$\geq 0.25$
7 events in $\leq 33$ patients	$\geq 9.21$	$\geq 0.23$

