## 5 **TREATMENTS**

### 5.1 STUDY TREATMENT: PROSTVAC-V/F

Subjects must start study drug within 120 days after surgery.

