## 5.2 SELECTION AND TIMING OF DOSE FOR EACH SUBJECT

### 5.2.1 PROSTVAC-V/F Treatment

All subjects will receive PROSTVAC V/F in the same dose and schedule.

**Drug Administration:** Doses of PROSTVAC-V/F will be drawn into labeled syringes by a research pharmacist or designee for use by the clinic staff. PROSTVAC-V will be administered by the designated study staff once by subQ injection on one side (upper arm or upper outer thigh) on Day 1. PROSTVAC-F will be administered by the study staff six times by subQ injection on Days 15, 28, 57, 85, 113 and 141. Vaccination with PROSTVAC-F will begin on one side (upper arm or upper outer thigh), and subsequent immunization sites should be rotated to the opposite side and/or limb if possible. The doses will contain the following:

- 0.5 ml containing at least  $2 \times 10^8$  Infectious Units (Inf.U) PROSTVAC-V
- 0.5 ml containing at least  $1 \times 10^9$  Inf.U PROSTVAC-F

Subjects should be informed on how to care for the wound after each injection of the study agent.

**Dose Modification or Interruptions:** There will be no modification or delays in dosing of PROSTVAC V/F for toxicity. If there are unresolved toxicities related to PROSTVAC V/F at the time the next dose is due, the patient should be taken off study. PROSTVAC V/F treatment should be initiated within 120 days after prostatectomy. If there is a delay due to scheduling, within the  $+\text{-} 7$  days window, it will be at the investigator's discretion whether to have the subject continue.

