## 7.3 OFF-STUDY ASSESSMENTS

Off study assessments will consist of those procedures indicated for day 730 if the patient's participation ends at that time, or at any earlier time. These include:

- clinical examination (history and physical examination);
- assessment of toxicity or adverse events;
- CBCD;
- CMP
- bone scan and CT scan of abdomen, and pelvis (a Prostascint scan or MRI of abdomen, pelvis can be substituted). Scans will not be repeated at the off-study point if they have been performed in the preceding 2 months.
- PSA;

- total testosterone;
- research assessments
  - Blood samples-See Section 8 for details
  - Quality of Life questionnaires

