## 7.5 EFFICACY ASSESSMENTS

Efficacy assessments will primarily be performed by measurement of PSA and by physical assessment. Imaging studies (CT scans of the abdomen and pelvis, and bone scans) will be performed at baseline (up to 16 weeks prior to treatment) and at the end of the study (or within the preceding 2 months before end of study). Otherwise, scans will be performed only if clinically indicated for evaluation of relapse or off study. Additional forms of imaging (Prostascint scan, MRI) may be substituted for a CT scan of the abdomen and pelvis if clinically indicated. However, the imaging method used at baseline will be used for follow up scans. Compliance with therapy may be considered a component of the efficacy assessment. Compliance with PROSTVAC-V/F will be monitored at each visit by interviewing the patient and reviewing the infusion center records for administration.

Both primary and secondary efficacy assessment involve measurement of RFS. Recurrence will be defined as the occurrence of any of the following:

- Institution of new prostate cancer therapy
- First detection of a PSA level  $\geq 0.2$  ng/mL (confirmed  $> 30$  days later) after completion of all PROSTVAC V/F vaccine doses
- Development of radiographically-demonstrable metastases
- Death

RFS at two years will be met if a patient has met none of the above criteria two years post-surgery. RFS as a time to event endpoint will be measured as the time in days from surgery to any of the above conditions being met.

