**APPENDIX A: SCHEDULED PROCEDURES AND ASSESSMENTS**

		Days on study f														
Therapeutic trial procedures	Procedure c	Pre a	1 n	15	29	57	85	113	141	225	309	393	477	561	645	730 g
	Informed Consent	X c														
	Full Physical Exam	X														
	Focused Physical Exam															
	Full Medical History	X														
	Interim Medical History o															
	AE assessment															
	CBCD	X														
	CMP	X														
	PSA	X m														
	Testosterone	X														
	CRP	X														
	Lipid Panel															
	CT (abdomen/pelvis)	X b														
	Tc-bone scan	X b														
	HIV test	X i														
	Hep B and C testing	X i														
Treatment	PROSTVAC-V															
	PROSTVAC-F															
Correlative Research	FACT-P															
	AUA															
	SHIM															
	Social Determinants Questionnaire															
	Research blood e															
	Research FFPE tissue	X i														
	Optional Sub-study Consent	X d														
Optional Sub-Study	Trier Stress Test	X i														

- a. Screening Assessments ("Pre") may be done up to 30 days prior to registration unless otherwise noted.
- b. Radiographic assessments may be done up to 26 weeks prior to registration. PSA at screening is required to document eligibility for post-operative PSA and may be done greater than 30 days prior to registration.
- c. The informed consent for the main study can be obtained more than 30 days prior to registration but must be obtained before any research procedures are completed
- d. The optional sub-study consent must be obtained prior to conducting the Trier Stress Test. The optional sub-study is voluntary and does not impact the patient's ability to participate in the main therapeutic portion of the trial.
- e. See [section 8](#) for blood draw volume and tube type requirements.
- f. all specified times are +/- 7 days
- g. or off-study day
- h. follow up will begin after the last day of study drug administration.
- i. Research blood, social determinants questionnaire and quality of life questionnaires may be completed any time after informed consent is signed and prior to Day 1 drug administration.

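### No visit is tied to the surgery date, and Section 10.1 conflicts with the synopsis and Section 7.5 on whether a relapse first found after 24 months is a primary-endpoint failure

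*Combined protocol and SAP*

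**What the plan says.** **Clock for visits.** Appendix A numbers visits in days on study. The last three are Days 561, 645 and 730, and "all specified times are +/- 7 days". Section 5.2.1 gives PROSTVAC-V "once by subQ injection on one side (upper arm or upper outer thigh) on Day 1", so the visit clock starts at the first dose. Section 5.1 adds: "Subjects must start study drug within 120 days after surgery". The final visit is the Day 730 set in Section 7.3: "Off study assessments will consist of those procedures indicated for day 730".

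**Clock for the endpoint.** Section 10.1 states: "The primary endpoint will be a binary indicator of relapse status at the 2 year follow-up visit after prostatectomy". It does not say which scheduled visit that is. It prefers this to a time-to-event estimate because some patients will have "follow-up weeks to months after the 2 year anniversary of their surgery and recurrences defined at those later timepoints would not be captured" by Kaplan-Meier. Section 7.5, like the synopsis, says: "RFS at two years will be met if a patient has met none of the above criteria two years post-surgery". It times events in days from surgery. The 24/30 decision rule in Section 10.1 refers to men recurrence free at 24 months, and Section 4.1 follows men for two years after prostatectomy.

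**Benchmark.** The null of 0.60 is a two-year probability. For the 243-patient database, timed from prostatectomy, Section 10.1 reports: "The observed 1yr probability of RFS was 0.751 and the 2yr probability of RFS was 0.645". For E3886 it gives 0.73 at one year and 0.56 at two. Appendix B recalculates E3886 from prostatectomy by Kaplan-Meier.

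**The concern.** Two clocks are in use and nothing joins them. Section 10.1's reason for choosing a binary endpoint implies that relapses discovered after the anniversary should count. The other definitions imply that they should not. The same man can be scored either way, and the protocol does not say which text governs.

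The trial is open-label with one arm and 30 evaluable men, and the futility look (11 of 19) and the final cut (22 of 30) both turn on single patients. If the point stays open, the definition could be chosen after outcomes are known. If late relapses do count, the trial proportion covers more time from surgery than the 24-month rate it is tested against.

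**Working it through.** **1. Reproduce the plan's figures.** Exact two-stage binomial: continue if at least 12 of the first 19 are recurrence free, and reject if at least 22 of 30 are.
- At 0.60, the rejection probability is 0.0934.
- At 0.78, it is 0.8007.

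The stated 0.1 and 0.8 are met when status refers to 24 months.

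**2. Where the anniversary falls.** For a man dosed S days after surgery, Day 730 is 729 + S days after surgery. With S = 120 this is 849 days (27.9 months), or 856 days with the 7-day window. The anniversary (surgery + 730) is study day 731 − S, so it ranges from Day 611 to about Day 730.
- Day 730 ± 7 covers it for S of 8 or less.
- Day 645 ± 7 covers it for S from 79 to 93.
- Day 561 ± 7 (up to Day 568) never covers it.

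For S from 0 to 120 that is 9 + 15 = 24 of 121 possible start days. The other 97 leave the anniversary outside every window.

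**3. One man, two scores.** Take S = 62. Day 645 is 644 + 62 = 706 days after surgery (23.2 months). Day 730 is 729 + 62 = 791 days (26.0 months). If he is clear at the first visit and first found relapsed at the second, he is a failure if that second visit supplies the status and a success under Section 7.5.

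**4. Size, if post-24-month relapses count.** The documents give no hazard beyond 24 months, so the following are assumptions.
- The year-2 hazard from Section 10.1 continues: ln(0.751/0.645) = 0.152 per year and ln(0.73/0.56) = 0.265 per year, with a central value of 0.21.
- The hazard ratio is constant: ln(0.78)/ln(0.60) = 0.486.
- For a delay of d days, null = 0.60 × exp(−h·d/365) and alternative = 0.78 × exp(−0.486·h·d/365).

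For example, with d = 90 and h = 0.21, the null is 0.570 and the alternative 0.761.

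| Delay past 730 days from surgery | Null | Alternative | Power (range over the two hazards) | Rejection probability at the null |
|---|---|---|---|---|
| 0 | 0.60 | 0.78 | 0.80 | 0.093 |
| 42 | 0.59 | 0.77 | 0.76 (0.75–0.77) | 0.070 |
| 60 | 0.58 | 0.77 | 0.75 (0.73–0.76) | 0.061 |
| 90 | 0.57 | 0.76 | 0.72 (0.70–0.74) | 0.049 |
| 119 | 0.56 | 0.75 | 0.69 (0.66–0.72) | 0.040 |

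The 42-day row is the average wait for the next visit on 84-day spacing (645 − 561 = 84; half is 42). The 119-day row puts every man at the latest permitted start (849 − 730 = 119).

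**The case against.** **The power statement is correct as written.** This stands. A reader might infer that the trial does not deliver 80% power, but the documents do not support that as a flat statement. No section names Day 730 as the two-year visit, and most of the text points to 24 months. The loss appears only if later relapses count, and its size rests on assumed hazards.

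**Some men do have a visit at the anniversary.** This also stands. A reader might infer that no visit ever falls two years after surgery. Starts at 79 to 93 days, or within 8 days, are covered. The accurate statement is that no visit is anchored to surgery and most possible start dates miss.

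**The mismatch is harmless because it works against the vaccine.** Taken alone it is conservative, since the rejection probability at the null falls. A reader might go further and infer that the whole comparison is biased against the vaccine. That is not established, because entry requires PSA below 0.2 ng/mL up to 120 days after surgery, so the earliest failures cannot enrol. The historical clock starts at prostatectomy, the database admits persistently detectable PSA as a risk feature, and 17 of 98 E3886 men had detectable PSA.

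As an illustration, assume a constant year-1 hazard from the average one-year rate: −ln(0.7405) = 0.300 per year. For a start at 90 days:
- Conditioning on being event-free at entry moves 0.60 to 0.60/exp(−0.300 × 90/365) = 0.646.
- Reading 89 days late at 0.21 per year brings it to 0.614, with a rejection probability of about 0.12.
- Over starts at 60 to 120 days that probability is about 0.11 to 0.13. With status cut at 24 months it is 0.16 to 0.27.

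The sign of the net bias therefore depends on assumptions.

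**The shift is small beside the uncertainty in the null.** True: the null moves by about 0.01 to 0.04 in the central rows, while the two sources are 0.645 and 0.56. This limits the weight of the power figures. It does not settle how an individual man is scored.

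**Conclusion.** The point holds as an unresolved contradiction in the primary endpoint, not as a demonstrated failure of the design. The documents establish that visits run from first dose, that Day 730 can be 27.9 months after surgery, that the two-year visit is unnamed, and that Section 10.1's rationale conflicts with the synopsis, Section 7.5 and the 24-month decision wording.

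The firm consequence is that some men cannot be scored unambiguously, and near 22 of 30 one man can change the conclusion. The conditional consequence, if later relapses count, is power of about 0.76 for a 42-day delay, 0.72 for 90 days and 0.66 to 0.72 at the extreme. This rests on the year-2 hazards continuing and a constant hazard ratio. No net direction of bias against the historical controls should be claimed.

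Separately, Section 10.1 also prints a cut of 24 of 30. That gives power of about 0.50 even at 24 months and needs its own reconciliation. The figures here use the 22 of 30 rule.

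**What to change.** - Put one definition in the synopsis, Section 7.5 and Section 10.1. Primary status is set by event date, and failure is a qualifying event dated on or before 730 days after prostatectomy. Relapses first detected later do not change it; they enter the time-to-event analysis only. Use the same status for the 11 of 19 futility look.
- State that a first PSA of 0.2 ng/mL or more on or before the cut-off, confirmed more than 30 days later, counts at its first-detection date, even when the confirmation comes after the cut-off.
- Re-time the nearest existing follow-up PSA to surgery + 730 days (± 7), or name the visit that supplies the status. End-of-study imaging can stay at Day 730.
- Present the two-year Kaplan-Meier estimate, already planned in Section 10.1, as the like-for-like comparison with the historical rates.
- If the Day 730 reading is preferred, restate the null and the power for that time from surgery.

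The cost is protocol wording and one existing visit re-timed per man, with no added patients. The change makes scoring unambiguous and restores the setting in which 0.80 and 0.093 were calculated. It does not resolve the entry-PSA difference from the historical series, which should be acknowledged when the result is interpreted.

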#### **4.7 DISCONTINUATION OF SUBJECTS FROM STUDY**

Subjects must discontinue study treatment and withdraw from the study or optional sub-study for any of the following reasons:

- Withdrawal of informed consent (subject's decision to withdraw for any reason)
- PCa relapse at any time after completion of PROSTVAC administration (see 7.5 for definition)
- Any clinical adverse event (AE), laboratory abnormality, or intercurrent illness which, in the opinion of the investigator, indicates that continued participation in the study is not in the best interest of the subject
- Termination of the study by BNI
- Loss of ability to freely provide consent through imprisonment or involuntarily incarceration for treatment of either a psychiatric or physical (e.g., infectious disease) illness
- Initiation of any form of non-protocol cancer treatment
- Initiation of scheduled narcotics for pain treatment

- Unacceptable toxicity defined as any grade 3-4 possibly or definitely related non-hematologic toxicity that does not improve to grade 1 or resolve within 28 days or any possibly or definitely related grade 3-4 hematologic toxicity that does not improve to grade 1 or resolve with 14 days.

General or specific changes in the patient's condition render the patient unacceptable for further treatment in the judgment of the investigator.

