### **10.4 POPULATIONS FOR ANALYSES**

Subjects evaluable for toxicity or efficacy will be those who receive at least one dose of PROSTVAC-V.

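### Section 10.1 lets dosed dropouts be replaced although 10.4 counts every dosed man as evaluable, and no rule covers an unknown 2-year status; if loss is informative, the 22/30 rule could exceed its 0.10 type I error

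*Combined protocol and SAP*

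**What the plan says.** All references are to the combined protocol and SAP.

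- **Endpoint (10.1):** "The primary endpoint will be a binary indicator of relapse status at the 2 year follow-up visit after prostatectomy".
- **Replacement (10.1):** "Patients who drop out will be replaced for up to 4 patients". The sentence draws no line between dosed and undosed men. Men who choose to stop treatment before an event but wish to stay are followed to 24 months under intent-to-treat and are not replaced.
- **Missing 2-year data (10.1):** such men "will be censored at the last visit at which they were known to be recurrence-free". This directly follows the sentence introducing the time-to-event analysis, which is not used for primary inference.
- **Population (10.4):** "Subjects evaluable for toxicity or efficacy will be those who receive at least one dose of PROSTVAC-V".
- **Leaving the study (4.7):** "Subjects must discontinue study treatment and withdraw from the study or optional sub-study for any of the following reasons". The list includes adverse events or intercurrent illness, unacceptable toxicity and scheduled narcotics for pain. Section 5.2.1 adds that with an unresolved related toxicity when the next dose is due, "the patient should be taken off study".
- **Decision rule (10.1):** stop for futility at 11 or fewer of 19; otherwise reject at 22 or more of 30 evaluable men. Planned enrolment is 33, allowing for 10% dropout.

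**The concern.** The conclusion of this single-arm trial rests on one count in about 30 men, and the plan gives two answers to who is counted. Under 10.4 a dosed man who leaves stays in the denominator. Under 10.1 he can be replaced and disappears from it. Both looks, at 19 and at 30, are defined for evaluable men, so both depend on which section is followed. Left open, the choice could be made after outcomes are known.

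The protocol's own rules produce such men. Sections 4.7 and 5.2.1 remove men from the study for toxicity, illness or narcotics, and the intent-to-treat sentence in 10.1 is worded for men who choose to stop. A man removed while event-free has one off-study assessment (7.3), after which the plan does not provide for his 2-year status.

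Informative loss is plausible, though not shown. One route is the PSA criterion in 7.5, which counts a rise only after all vaccine doses are complete. Read literally, a man whose PSA rises during dosing and who leaves before finishing has no PSA event, and could be replaced rather than counted. If replaced men would have relapsed more often than average, the men left look better than the population treated, and a false positive becomes more likely.

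**Working it through.** **Inputs from 10.1.** Null and alternative 2-year RFS: "increase in the probability of RFS from 0.6 to 0.78". Error rates: "Assuming a one-sided alpha = 0.1, with 30 evaluable patients, we have 80% power to detect this difference". Rule: stop at 11 or fewer of 19, reject at 22 or more of 30. Enrolment 33; replacements up to 4.

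**Input not in the documents.** The share *s* of replaced men who would have relapsed by 2 years. It is an assumption, varied from 0 to 100%; 40% is the uninformative value when overall RFS is 0.60.

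**Step 1. Reproduce the stated design.** With success probability *p*,

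P(reject) = Σ over x = 12 to 19 of P(Bin(19, p) = x) × P(Bin(11, p) ≥ 22 − x).

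At p = 0.60 this is 0.0934; at p = 0.78 it is 0.8007. The stated 0.1 and 0.8 are confirmed.

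**Step 2. RFS among the men retained.** Hold RFS among all *N* dosed men at 0.60 and replace *d* of them:

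p_ret = (0.60 N − d(1 − s)) / (N − d).

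Example, N = 34, d = 4, s = 60%: (20.4 − 1.6)/30 = 0.627. Example, N = 33, d = 3, s = 60%: (19.8 − 1.2)/30 = 0.620.

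**Step 3. Type I error of the 11/19, 22/30 rule at p_ret.**

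| Share of replaced men who would relapse | 4 of 34: p_ret | alpha | 3 of 33: p_ret | alpha |
|---|---|---|---|---|
| 0% | 0.547 | 0.029 | 0.560 | 0.039 |
| 20% | 0.573 | 0.053 | 0.580 | 0.062 |
| 40% (uninformative) | 0.600 | 0.093 | 0.600 | 0.093 |
| 50% | 0.613 | 0.12 | 0.610 | 0.11 |
| 60% | 0.627 | 0.15 | 0.620 | 0.14 |
| 75% | 0.647 | 0.21 | 0.635 | 0.18 |
| 100% | 0.680 | 0.34 | 0.660 | 0.26 |

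**Step 4. Following 10.4 instead.** If all dosed men are counted but the cut-off stays at 22, alpha at p = 0.60 is 0.247 with 33 dosed and 0.299 with 34, so the cut-off must move with the number dosed. Keeping the 11/19 look, the smallest cut-offs holding alpha at or below 0.10 are:

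| Dosed | Reject at | alpha | power at 0.78 |
|---|---|---|---|
| 30 | 22 | 0.093 | 0.80 |
| 31 | 23 | 0.073 | 0.77 |
| 32 | 24 | 0.057 | 0.74 |
| 33 | 24 | 0.091 | 0.82 |
| 34 | 25 | 0.072 | 0.80 |

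**Step 5. Price of counting unknown as failure.** With 33 dosed and 3 unknown, 24/33 needs 24 successes among 30 known men. If loss is uninformative, P(Bin(30, 0.60) ≥ 24) = 0.017 and P(Bin(30, 0.78) ≥ 24) = 0.499.

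**The case against.** Several points on the other side are sound.

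- **Censoring.** A reader might infer that the plan censors a yes/no endpoint. The text does not support that: the censoring sentence follows the introduction of the supplementary time-to-event analysis, where it is ordinary practice. The gap is that nothing equivalent is said for the binary endpoint.
- **Known failures.** A reader might infer that men who start new prostate cancer therapy, or who die, are lost. They are not: 7.5 counts both as relapse. Section 7.3 also calls for PSA, CT and bone scan at an early exit, with recent scans accepted, so some early disease is caught. The exposure is limited to men who leave event-free and whose later status is unknown.
- **Direction.** No section gives outcomes for dropouts. With uninformative loss alpha does not move, and with favourable loss it falls.
- **The other cut-off.** Section 10.1 and the synopsis also state a rule of at least 24 of 30. Under it, the 4-of-34 scenarios at 60%, 75% and 100% give 0.034, 0.054 and 0.110, so the inflation applies to the two-stage rule. That rule is the one stated with the interim design and the one that reproduces the planned error rates; 24/30 has power of only 0.499.
- **Replacement may mean undosed men.** The synopsis explains the gap from 33 to 30 as in-evaluability, which together with 10.4 could mean men never dosed. Section 10.1 speaks of dropouts and does not say so; that is the clarification needed.
- **Three versus four.** Up to 4 replacements against 3 spare places is housekeeping: 4 is a ceiling, and 30/0.9 = 33.3.

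**Conclusion.** The point holds in a conditional form. Sections 10.1 and 10.4 conflict on whether a dosed dropout is counted, 4.7 and 5.2.1 create such men, and no rule assigns an unknown 2-year status to the primary proportion. As written, the primary count can be taken in more than one way.

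A reader might go further and conclude that dropouts are likely failures and that the rule has lost its error rate. The documents do not show that. Type I error passes 0.10 only if replaced men relapse more than average. A modest excess is enough (50% against 40% gives 0.12 with 4 of 34, 0.11 with 3 of 33), and the upper end of 0.34 needs every replaced man to be a relapse. The figures assume overall RFS of exactly 0.60 among dosed men, independent outcomes, the same retained RFS at both looks, and the 11/19, 22/30 rule.

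**What to change.** 1. **Replacement (10.1).** Limit it to men who never received PROSTVAC-V.
2. **Follow-up (4.7, 5.2.1, 10.1).** Reconcile these sections so that men who stop treatment for any reason other than withdrawn consent stay in PSA and therapy follow-up to 24 months after surgery. The treatment-stopping criteria are not at issue and stay as they are. Appendix A note p already allows local PSA and phone contact for non-local men. State also how the PSA criterion in 7.5 applies to men who never complete all doses; otherwise the added follow-up may yield no PSA events.
3. **Primary population (10.1, 10.4).** Use all dosed men in both sections, with the cut-offs by number dosed in the step 4 table.
4. **Unknown status.** State how any remaining unknown enters the interim count of 19 and the final count. Report a missing-as-failure analysis beside a complete-case analysis.

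**Cost.** Protocol and SAP wording, plus a small number of PSA results and calls. Power falls below the planned 80% if 31 or 32 men are dosed (0.77, 0.74). Making missing-as-failure the primary rule is not a minor conservatism: at 24/33 with 3 unknown and uninformative loss, power is about 0.50. It should be the primary rule only if follow-up keeps unknowns rare.
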